4.1 Study Medication Prescribing/Authorization

Medical cannabis is accessible to subjects via different authorization or prescription pathways, in different regional jurisdictions. Authorization and prescription are the two most common pathways.

In Canada, Spectrum Therapeutics products are authorized via the physician specifying the amount (in grams) of THC and/or CBD, and the subject is free to choose the product, licensed producer, and formulation on their own. Likewise, subjects have the freedom to switch from one product or producer to another, at will.

In other countries, such as Germany, medical cannabis products are prescribed, and physicians are specific in this process regarding parameters such as the licensed producer, mode of administration, and cannabinoid content (THC:CBD).

This protocol does not assign a specific intervention. The prescription of medical cannabis is decided by the subject and his or her physician prior to enrolling the subject in the study. The principal investigator has no control over the prescribing/authorization or administration of the cannabis product.

4.2 Study Medication: Cannabinoid Content Calculation

On entering study medication information into *REDCap Cloud*, the preprogrammed algorithm will calculate the intake amount of mgs of THC and CBD for all formulations, and whether it was inhaled or ingested. Only limited data exist on the plasma concentration of circulating cannabinoids and their metabolites resulting from inhalation of cannabis products. It is known that factors influencing this include, but are not limited to, pattern of smoking or vaping (length of inhalation), as well as the flower combustion temperature. It is possible that these data may be calculated in retrospect (unlike other formulations that will allow for real time mg calculation), if more structured studies are conducted to evaluate the cannabinoid intake from smoked and/or vaped products, from different flower varieties.

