4. STUDY MEDICATION

For the purposes of this study, subjects enrolled will have been prescribed/authorized Spectrum Therapeutics products that are commercially available in participating countries. It is important to note that product availability varies from country to country. No country except Canada, has access to the full ST medical portfolio (e.g., only flowers are available in Germany).

The full repertoire of Spectrum Therapeutics products is outlined here (see Figure 1). It encompasses six “colors” (order from Red to Yellow follows the descending THC:CBD ratio), and five types of formulations: soft gels, spray*, oil, flowers and vapes). Refer to webpage for the most up to date products available per country <https://www.spectrumtherapeutics.com/canada/en/patients/products>.

Figure 1. Repertoire of Spectrum Therapeutics Products.

Cannabinoid Content for Spectrum Therapeutics Products			
Spectrum Product	Percentage of THC & CBD per gram of weight Dried flower (%)	Milligram of THC & CBD per milliliter of Oil (mg/ml)	Milligram of THC & CBD per Soft gel (mg)
Red 	(17-23) THC : (< 0.7) CBD	(26.3) THC : (<1) CBD	(2.5-10) THC : (<1) CBD
Orange 	(10-14) THC : (<1) CBD	NA	NA
Purple 	(8-11) THC : (< 0.7) CBD	NA	NA
Blue 	(6-10) THC : (8-11) CBD	(10) THC: (12-15) CBD	(2.5 – 10) THC : (1.75-15) CBD
Green 	(4-7) THC: (7-10) CBD	NA	NA
Yellow 	(<1) THC : (10-14) CBD	(<1) THC : (20) CBD	(<1) THC: (5-20) CBD

*Spray formulation is the most recent addition to the formulations and not yet featured on the web site.

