Benzodiazepines Dosing Information

Name of drug _____

Daily dose of [baseline_visit][benzo1_name](total mg per day) _____

Check to add additional benzodiazepine medications

Name of drug _____

Daily dose of [baseline_visit][benzo2_name] (total mg per day) _____

Check to add additional benzodiazepine medications

Name of drug _____

Daily dose of [baseline_visit][benzo3_name] (total mg per day) _____

Opioid Dosing Information

Please enter MME (total daily morphine equivalent dose in mg) _____

Other Medication Information

Please indicate name of other drugs not included in the above classes _____

Daily dose (total mg per day), if available _____

ST Regimen Canada

[figure not shown]

Please enter in the table below total daily amount of Spectrum Therapeutics products consumed. Please be conscious of the units provided:

Inhaled cannabis = total number of inhalations per day

Ingested oils = total mL per day

Spray format = total number of sprays per day

Capsules & edibles = total number of capsules or total number of chocolate bar squares per day

	Inhaled Formats (dried flower, extract vaporizers) -- report daily total number of inhalations	Ingested Oil Formats - report daily total number of mLs	Spray Formats - report daily total number of sprays	Low Potency Capsule & Edible Formats - report daily total number of low-potency capsules (i.e. 2.5 mg), number of chocolate bar squares, etc.	High Potency Capsule Formats - report daily total number of high-potency capsules
Red (examples include Spectrum #1-4; Tweed Bakerstreet, Highlands, Houdstooth, Donegal; LBS Sunset)	 inhalations  	 mL  	 sprays  	 capsules  	 capsules  
Orange	 inhalations  		 sprays  		
Purple (examples include LBS Ocean View)	 inhalations  		 sprays  		
Blue (examples include Tweed Penelope)	 inhalations  	 mL  	 sprays  	 capsules  	 capsules  
Green (examples include Tweed Argyle)	 inhalations  	 mL  	 sprays  	 capsules  	 capsules  

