Yellow (examples include Tweed CBD Softgels)	 inhalations  	 mL  	 sprays  	 capsules  	 capsules  
Spectrum Clear (or White)		 mL  			

You indicated that your patient has been recommended an inhaled format. Please identify their most common method of administration.

(inhal_admin)

[Branching logic exists]

- Smoked
- Dried flower vaporizer (e.g. Stroz and Bickel, PAX)
- Extract vaporizer (e.g. vape pen cartridge)

Do you or your patient know the temperature set point of the vaporizer (in °C)

(inhal_vape_Y/N)

[Branching logic exists]

- Yes
- No

If known, please provide the temperature set point of your patient's vaporizer (in °C) _____

(inhal_vape_temp)

(125 / 300)

[Branching logic exists]

Calculated, approximated total daily dose of THC and CBD (in mgs)

	THC	CBD
Inhaled	
(inhal_THC)
  
View Equation
	
(inhal_CBD)
  
View Equation

Ingested	
(ingest_THC)
  
View Equation
	
(ingest_CBD)
  
View Equation

Patient reported outcomes

BPI

Throughout our lives, most of us have had pain from time to time (such as minor headaches, sprains, and toothaches). Have you had pain other than these everyday kinds of pain today?

- Yes
- No

Please select the number (0= no pain, 10= pain as bad as you can imagine) that best describes your pain at its worst in the last 24 hours.

- 0
- 1
- 2
- 3
- 4
- 5
- 6
- 7
- 8
- 9
- 10

Please select the number (0= no pain, 10= pain as bad as you can imagine) that best describes your pain at its least in the last 24 hours.

- 0
- 1
- 2
- 3
- 4
- 5
- 6
- 7
- 8
- 9
- 10

Please select the number (0= no pain, 10= pain as bad as you can imagine) that best describes your pain on the average.

- 0
- 1
- 2
- 3
- 4
- 5
- 6
- 7
- 8
- 9
- 10

Please select the number (0= no pain, 10= pain as bad as you can imagine) that best describes how much pain you have right now.

- 0
- 1
- 2
- 3
- 4
- 5
- 6
- 7
- 8
- 9
- 10

Please select the number (0= does not interfere, 10= completely interferes) that best describes how, during the past 24 hours, pain has interfered with your: **General Activity**

- 0
- 1
- 2
- 3
- 4
- 5
- 6
- 7
- 8
- 9
- 10

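### Section 4.2 is inconsistent on whether inhaled THC/CBD mg is calculated at entry, and the Canadian forms as printed cannot give the inhaled mg of a subject who uses both flower and extract

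*Protocol*

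**What the plan says.** Protocol Section 4.2 opens by stating that, on data entry, "the preprogrammed algorithm will calculate the intake amount of mgs of THC and CBD for all formulations", together with whether the product was inhaled or ingested. It then notes how little is known about plasma levels after inhalation, and adds: "It is possible that these data may be calculated in retrospect (unlike other formulations that will allow for real time mg calculation"), provided that further studies of intake from smoked or vaped products are done.

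Appendices 1 to 3 print the Canadian regimen form. Its inhaled column reads "Inhaled Formats (dried flower, extract vaporizers) -- report daily total number of inhalations", with one cell for each of six colours. Below the table, for inhaled products, the form says "Please identify their most common method of administration", with three options: smoked, dried flower vaporizer and extract vaporizer. It then asks for the vaporizer temperature where known. A block headed "Calculated, approximated total daily dose of THC and CBD (in mgs") follows, with inhaled and ingested fields, each with an equation that is not printed.

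Section 7.1 makes average daily THC and CBD in mg, and its change over time, part of the primary endpoint (physician selection) and of the first secondary endpoint (subject selection). Section 4 lists flowers and vapes as separate formulations. It says that only Canada has the full portfolio, and gives as an example that "only flowers are available in Germany".

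**The concern.** There are two linked problems.

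First, a reader of Section 4.2 cannot tell whether the inhaled mg value stored at entry is the analysis value, a provisional one, or something deferred to a later calculation. It feeds the main endpoints, so its status should be clear.

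Second, a conversion from inhalations to mg needs to know which product was inhaled. The printed form adds flower and extract inhalations together before recording them. If the split is not captured elsewhere, no later analysis decision can restore it. A change in the mix of formats could then look like a dose change that did not happen, or hide one that did. The same table already separates low- and high-potency capsules, so this principle is applied to one formulation and not to the other.

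**Working it through.** **Part A: the statements side by side.**

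1. Section 4.2, first sentence: mg is calculated on entry for all formulations, inhaled ones included.
2. Section 4.2, last sentence: inhaled data may be calculated later, in contrast to other formulations, for which mg is available in real time.
3. Appendices 1, 2 and 3: inhaled THC and CBD mg fields are calculated on the form and labelled as approximated.

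Statements 1 and 3 agree. The parenthesis in statement 2 excludes inhaled products from what 1 and 3 provide. The condition attached to statement 2 concerns intake, which is the quantity that statement 1 says is calculated.

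**Part B: can inhaled mg be derived from the printed inputs?**

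Let n_f and n_e be daily inhalations of flower and extract in one colour, and m_f and m_e the mg per inhalation.

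- Needed: true mg = n_f × m_f + n_e × m_e.
- Recorded: N = n_f + n_e, plus one most common method for the whole regimen.

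One recorded sum cannot give two unknown counts. The mg follows from N alone only if m_f = m_e. A subject with flower in one colour and extract in another is not resolved either, because the method is asked once and not by colour. For a single-method user, N and the method are enough, and a revised factor can be applied later.

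**Illustration of size.** The protocol gives no mg per inhalation, and the content table in Section 4 has no vape column. I therefore assume r = m_e / m_f. Let s be the extract share of inhalations, with flower the recorded method and every inhalation costed as flower:

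calculated / true = 1 / [(1 − s) + s × r]

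| s | r = 0.5 | r = 1 | r = 2 | r = 3 |
|---|---|---|---|---|
| 0.2 | 1/0.9 = 1.11 (+11%) | 1.00 (0%) | 1/1.2 = 0.83 (−17%) | 1/1.4 = 0.71 (−29%) |
| 0.4 | 1/0.8 = 1.25 (+25%) | 1.00 (0%) | 1/1.4 = 0.71 (−29%) | 1/1.8 = 0.56 (−44%) |

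**Change over time**, at a constant inhalation count and with each visit costed at its recorded method (flower = 1, extract = r):

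- 60:40 flower/extract moving to 40:60. At r = 2, calculated 1 to 2 = +100%; true 1.4 to 1.6 = +14%. At r = 0.5, calculated 1 to 0.5 = −50%; true 0.8 to 0.7 = −12.5%. At r = 1, both are 0%.
- All flower moving to 60:40. Calculated 1 to 1 = 0%; true +40% at r = 2 (1 to 1.4) and −20% at r = 0.5 (1 to 0.8).

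If the unprinted equation ignores the method and applies one factor to every inhalation, both moves show as 0%, which is right only at r = 1.

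With separate counts and a fixed factor per format, this weighting error is zero for any r.

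**The case against.** **Section 4.2 may only be loosely worded.** The deferred data can be read as plasma levels, since the two preceding sentences are about plasma concentration and what affects it. On that reading the first sentence and the forms agree, and only systemic exposure is postponed. This is a fair reading and softens the conflict. It does not remove it, because the parenthesis contrasts inhaled products with others on mg calculation, not on plasma levels.

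**The printed forms are visibly incomplete.** The closing note of Appendix 4 refers to a question in the regimen tables, on whether the patient still takes the sponsor's products, that does not appear in the printed tables. Table 1 schedules additional cannabis consumption at subject follow-ups, yet printed Appendix 3 has no such item. Figures and equations are not shown, and only the Canadian form is reproduced. A reader might infer that the split is never recorded anywhere. The document does not support that; it supports only that the printed inputs do not contain it.

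**The link to the primary endpoint is partial.** That endpoint is physician selection. Section 4.1 says that in Canada the physician authorizes an amount and the subject chooses product and formulation, so the format mix there is largely the subject's choice. A reader might infer that the primary endpoint as a whole is compromised. That is not supported: the problem concerns one subgroup, and it bears at least as much on the secondary endpoint.

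**Inhaled mg is approximate in any case.** The forms say so, and the content ranges in Section 4 are wide: Red flower at 17 to 23% THC is 20% ± 3 points, or ± 15% around the midpoint. This limits how much precision the fix buys. It does not excuse an avoidable error that moves with the product mix.

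**Conclusion.** The point holds in a limited form. Section 4.2 is internally inconsistent, and its parenthesis conflicts with the calculated inhaled fields on the forms. As printed, the Canadian forms do not allow inhaled mg/day, or its change, to be correctly derived for a subject who uses both flower and extract, unless the two carry equal mg per inhalation.

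The scope is users of both inhaled formats where both are sold. Canada is stated to have the full portfolio and Germany only flower; the position in the other countries is not given. Single-method users, ingested mg and the inhaled/ingested route are not affected.

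The size cannot be derived from the protocol. The percentages above rest on assumed values of r and s, and only show that the error can go either way and vanishes at r = 1. The conclusion on derivability does not depend on those values, but it does depend on the live eCRF having no split beyond what is printed. This merits correction during the study, because an analysis plan could choose a conversion factor but could not recover counts that were added together at entry.

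**What to change.** 1. **Reword Section 4.2** so that it agrees with the forms: inhaled mg is an approximation calculated at entry that may be revised if better conversion data appear, and only systemic exposure is deferred, if that is the intent.
2. **Check the live eCRF.** Unless it already does so, split the inhaled column in Appendices 1 to 3 into dried flower and extract vaporizer for each colour in which an extract is sold. Apply a format-specific factor, and keep the raw counts so that a revised factor can be reapplied.

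The cost is one paragraph of text, an update to the programmed equation, and at most 6 colours × 3 forms = 18 extra cells, blank unless used. The number is smaller if some colours have no extract, which the protocol does not say. Two limits remain: data already entered in the pooled column stay unsplit, and smoked and vaporized flower still share one method field.

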4.3 Study Medication Safety Information

Cannabis and cannabinoids are generally considered to be well-tolerated, although there is a large degree of individual difference in the side effects seen. A review of medical cannabis trials found that 96.6% of side effects were not serious, with the most common side effects of acute use being²²:

- Somnolence
- Dizziness
- Drowsiness
- Fatigue
- Tachycardia (increased resting heart rate)
- Temporary impairment of sensation and body functions
- Intoxication or feeling “high”
- Nausea
- Vomiting
- Cough
- Abdominal Pain

Withdrawal symptoms from chronic use of cannabis can occur, usually within 1-2 days following discontinuation. The most common withdrawal symptoms include irritability, anxiety, sleep difficulties, craving, headache, restlessness, and anger or aggression, which usually resolve within 1-2 weeks.

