Given a continuous enrollment design, the study will include two enrollment milestones over the 2-year study period. Milestone 1, targeted for the end of year 1 will be to recruit 750 subjects. Milestone 2, targeted for the end of year 2 will be to recruit 750 subjects. To enroll a total of up to 1500 subjects. The number of subjects may vary based on the real-life use of ST products. Sites will be recruited from countries where ST products are available: Canada, United Kingdom, Germany, and Australia. Sites from additional countries may be included as ST products are rolled out in those countries and based on site feasibility.

The present study has an observational design that poses low-burden for subjects, as the number and frequency of in-clinic (telemedicine) visits represent those necessary for adequate monitoring of treatment for chronic pain and at-home follow-ups will be completed using a simple online app and take no longer than 15 minutes to complete. On this premise, we did not restrict the sample size based on an estimated minimum required sample. Furthermore, the observational nature of the primary endpoint (daily average dose [in mg] of THC and CBD and mode of administration [inhaled or ingested]), did not permit an a priori power analysis to estimate sample size. A sample size of 1500 subjects is consistent with similar previous observational registry studies.

Table 1. Schedule of Events

	Day 1	Month 1 (+/-7d)	Month 2 (+/-7d)	Month 3 (+/-7d)	Month 4 (+/-7d)	Month 6 (+/-7d)	Month 8 (+/-7d)	Month 10 (+/-7d)	Month 12 (+/-7d)	Un-scheduled visit
	Physician Baseline Visit	Subject-verified Follow-up 1	Physician Follow-up 1	Subject-verified Follow-up 2	Physician Follow-up 2	Subject-verified Follow-up 3	Physician Follow-up 3	Subject-verified Follow-up 4	Physician Follow-up 4	
Electronic Informed consent form (eICF)	X									
Pregnancy Test	X									
Review eligibility criteria check list	X									
Create subject REDCap Cloud account	X									
Demographics	X									
Concomitant medications	X		X		X		X		X	X
Chronic Pain Classification	X									
Cannabis experience	X									
Treatment goal	X									
ST treatment regimen	X	X	X	X	X	X	X	X	X	X
Additional cannabis consumption		X		X		X		X		
BPI-SF ¹	X	X	X	X	X	X	X	X	X	X
EQ5D-5L ²	X	X	X	X	X	X	X	X	X	X
PGI-C		X	X	X	X	X	X	X	X	X
CGI-I			X		X		X		X	X
Subject AE ³ log		X		X		X		X		
Physician AE ³ form			X		X		X		X	X
ST discontinuation assessment										X
Exit assessment										X

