3. STUDY DESIGN

3.1 Description of the Study

The present study is a prospective, observational registry designed to generate real-world data on the physician-recommended use of ST products to manage chronic pain in countries where these products are commercially available. The study will enroll up to 1500 subjects from 50-150 sites in geographic regions of ST product distribution over a two-year period. Physicians will recruit subjects during routine care visits and assess whether subjects with chronic pain are candidates for medical cannabis treatment. Once enrolled, subjects will be followed for 1 year to collect data on demographics, chronic pain classification, cannabis experience, treatment goals, concomitant medication(s), ST treatment regimen, clinical assessment, subject-reported outcomes, and safety.

The study includes five physician-verified visits (baseline, 2, 4, 8, and 12 months), and four at-home subject-verified follow-ups (months 1, 3, 6, 10). Physician verified follow ups can be conducted in person or via telemedicine. Additionally, should there be a need, according to the physician's judgement, there may be other unscheduled visits, either in-clinic, or via telemedicine. All data will be collected using *REDCap Cloud* via online eCRFs. The study time-points were selected based on the typical timeframe of titration in routine care, and adverse event (AE) emergence for the use of cannabis products in new subjects; a majority of titration occurs within the first month of taking a new cannabis product²⁹. Visits were also spaced out so that subject retention may be maximized, and treatment adjusted in a timely manner. Later time-points are designed to capture longer-term treatment-related outcomes while screening for AE emergence and medication use changes in the long term.

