In the event of ST treatment discontinuation, or study dropout, physicians will be asked to follow-up with subjects to complete the ST Discontinuation Assessment and Exit assessment (Appendix 4). Based on physician answers to ST Discontinuation Assessment, subjects will either stay enrolled in the study (e.g., discontinue all cannabis treatment, but continue to be monitored by site physician for chronic pain), or be withdrawn (e.g., unwilling to stay in the study, switched cannabis licensed producer).

A complete schedule of events is provided in **Table 1**.

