6.3 Subject Withdrawal from Study Participation

Subjects are free to withdraw from the study at any time. Subjects who start taking medical cannabis from another licensed producer or withdraw consent for study participation will be contacted by the site physician or study site personal to complete an Exit assessment as soon as possible.

Subjects that have received ST products and started using them for treatment of chronic pain, will be entered in the data analysis population, unless they have withdrawn consent together with withdrawing from the study. This is described in more detail, in the Statistical Analysis Plan.

The site physician, by joining the study, confirms commitment to subject retention through coaching, counseling, and education.

The site physician may withdraw a subject from the study in the following circumstances:

- Subject experiences a serious adverse event (SAE) or other safety concerns.
- Subject does not benefit from ST product treatment.
- Subject meets any exclusion criteria.
- Noncompliance with the study protocol.
- Administrative reasons or study termination (e.g., Sponsor decision).
- Other factors determined by the physician to affect the eligibility of subjects to continue.

A record of the reason for withdrawal will be maintained for reporting and publication. Subjects who are withdrawn or removed from the study will be replaced if the study is still in enrollment.

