[Branching logic exists]

If known, please provide the temperature set point of your patient's vaporizer (in °C) _____

(inhal_vape_temp)
(125 / 300)
[Branching logic exists]

Calculated, approximated total daily dose of THC and CBD (in mgs)		
	THC	CBD
Inhaled	(inhal_THC)  View Equation	(inhal_CBD)  View Equation
Ingested	(ingest_THC)  View Equation	(ingest_CBD)  View Equation

Side Effects

Does your daily dose include any side effects (e.g. nausea, dry mouth, drowsiness, euphoria, etc.)?

- Yes
- No

You indicated that you experience side effects from your daily dose. Please indicate which side effects you experience (check all that apply)

- Nausea
- Dry Mouth
- Dizziness
- Somnolence (i.e. sleepiness/drowsiness)
- Euphoria
- Other

Please describe the 'other' side effects that you experienced

Subject Adverse Event Reporting

AE diary

Since you have been taking Spectrum Therapeutics medical cannabis products, have you experienced any side effects? Please include any side effects you have experienced, regardless of whether you believe they are related to medical cannabis.

- Yes
- No

Please describe in as much detail the adverse event (side effect) that you experienced.

Adverse events, symptoms, start date/end date, event(s) chronology, treatments, outcome.

PGI-C

Global Impression of Change

Since the start of Spectrum Therapeutics treatment, my overall symptom status is:

(best describe how your symptom is now, compared with how it was before you began taking medical cannabis)

- Very Much Improved
- Much Improved
- Minimally Improved
- No Change
- Minimally Worse
- Much Worse
- Very Much Worse

Patient reported outcomes

BPI

Throughout our lives, most of us have had pain from time to time (such as minor headaches, sprains, and toothaches). Have you had pain other than these everyday kinds of pain today?

- Yes
- No

Please select the number (0= no pain, 10= pain as bad as you can imagine) that best describes your pain at its worst in the last 24 hours.

- 0
- 1
- 2
- 3
- 4
- 5
- 6
- 7
- 8
- 9
- 10

Please select the number (0= no pain, 10= pain as bad as you can imagine) that best describes your pain at its least in the last 24 hours.

- 0
- 1
- 2
- 3
- 4
- 5
- 6
- 7
- 8
- 9
- 10

Please select the number (0= no pain, 10= pain as bad as you can imagine) that best describes your pain on the average.

- 0
- 1
- 2
- 3
- 4
- 5
- 6
- 7
- 8
- 9

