Appendix 5 Exit Assessment

Exit Assessment

Confirm Study Exit

Please check the box to confirm the withdrawal of this patient from the study.

EXIT the Study

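### No adverse-event contact is defined after exit, so withdrawal symptoms that begin after the last dose go uncollected in subjects withdrawn at or soon after stopping

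*Protocol*

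**What the plan says.** Section 4.3 describes a withdrawal syndrome with its own timing: "Withdrawal symptoms from chronic use of cannabis can occur, usually within 1-2 days following discontinuation". It lists the typical symptoms, "which usually resolve within 1-2 weeks".

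Section 3.1 sets the contacts: "five physician-verified visits (baseline, 2, 4, 8, and 12 months), and four at-home subject-verified follow-ups (months 1, 3, 6, 10". When a subject stops ST or drops out, "physicians will be asked to follow-up with subjects to complete the ST Discontinuation Assessment and Exit assessment (Appendix 4".

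Table 1 marks those two assessments only in the "Un-scheduled visit" column. The Physician AE form is marked in that column too; the Subject AE log is not.

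The forms themselves contain the following:

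- **Appendix 4 (ST Discontinuation):** the stop date, the reason, the source of any continuing cannabis, and whether the subject wishes to stay. An adverse event appears only as one possible reason for stopping.
- **Appendix 5 (Exit):** one instruction and one box: "Please check the box to confirm the withdrawal of this patient from the study".
- **Appendix 2 (Physician AE form):** an open question with no time limit, and fields for onset and end dates.
- **Appendix 3 (Subject AE log):** "Since you have been taking Spectrum Therapeutics medical cannabis products, have you experienced any side effects", with a request to include events whatever their believed cause.

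Section 6.3 provides for prompt contact to complete the Exit assessment when a subject changes producer or withdraws consent. It also lets the physician withdraw a subject for a serious adverse event, another safety concern or lack of benefit. No contact after exit is described. A subject who stops ST but stays enrolled is told, at the end of Appendix 4, to keep the scheduled follow-ups.

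**The concern.** Most adverse events in this registry arise while the product is in use, and the follow-up forms are built for that. Withdrawal symptoms are different, because they can begin only after use ends. To record them, the plan needs at least one AE enquiry that looks back over the days after the last dose. For subjects whose participation ends with their treatment, the plan guarantees none.

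The safety objective in section 2.1.3 is the safety and tolerability of individual ST products. A low count of withdrawal symptoms could then reflect how data were collected rather than how subjects fared. No later analysis can restore events that were never asked about, so the place to act is the protocol and its forms.

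**Working it through.** The protocol gives no figure for AE capture after stopping, so there is none to reproduce. The check follows the two paths open to a subject who stops ST.

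**Path 1: withdrawn at or soon after stopping.** Take the stop as day 0.

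1. Usual onset is day 1 to 2 and usual resolution is within 7 to 14 days (section 4.3).
2. The last AE enquiry that Table 1 provides is the Physician AE form at the unscheduled visit. The protocol does not fix the day of that visit.
3. If the form is completed on day 0 or 1, the symptoms have mostly not begun. If it is completed a few days later, it sees only part of the course. It covers the whole usual course only if the visit happens about 14 days or more after the stop.
4. The number of planned AE contacts after exit is 0.

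**Path 2: stops ST but stays enrolled.** Scheduled contacts with an AE question fall at months 1, 2, 3, 4, 6, 8, 10 and 12 (section 3.1 and Table 1). Assume that stop dates are uniform over 12 months; the protocol does not say how they are distributed.

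- The gaps between contacts are 1, 1, 1, 1, 2, 2, 2, 2 months.
- Mean wait to the next contact = Σ(g²/2) / 12 = (4 × 0.5 + 4 × 2) / 12 = 10/12 = 0.83 months. In days this is 0.83 × 365/12 ≈ 25. The longest wait is 2 months.
- Median wait: a share 8x/365 of stops waits x days or fewer (for x up to one month). Setting this to 0.5 gives x = 365/16 ≈ 23 days.
- Physician visits alone (months 2, 4, 8, 12) have gaps of 2, 2, 4, 4 months. Mean wait = (2 + 2 + 8 + 8)/12 = 1.67 months, or about 51 days. The longest wait is 4 months.
- Sensitivity to the assumption: if all stops fall in months 0 to 4 the mean wait is 0.5 months (about 15 days). If all fall in months 4 to 12 it is 1 month (about 30 days).

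On path 2 an enquiry does take place and it looks back. The wait therefore measures delay in reporting, not events lost.

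**The case against.** The strongest reply is that the protocol already has an AE form at the stopping contact. Table 1 puts it beside the Discontinuation and Exit assessments. Sites may also learn of a stop some time later, since in Canada subjects may change product or producer freely (section 4.1), and the form would then look back over the days that matter. This stands in part. It means that some withdrawn subjects will be asked at a useful time. It does not mean that the plan secures this, because nothing sets the interval and nothing requires a second enquiry.

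A second reply is that the people most exposed are the ones retained: the protocol's own example of a subject who stays enrolled is one who gives up cannabis entirely. Those who change producer may continue cannabis and be at less risk. This stands, and it limits the point. It does not cover subjects unwilling to stay, or those withdrawn by the physician under section 6.3 who then stop.

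Several stronger readings are tempting and are not supported:

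- **That the rules cannot detect withdrawal symptoms at all, or that these are mostly missed in those who stay.** The physician form has no time limit and records onset and end dates, and the home log looks back.
- **That the share of stops with a contact inside the symptomatic period measures capture.** With 8 contacts and 14 days that share is 8 × 14/365 ≈ 31%. It describes the timing of contacts only; a resolved event can still be reported at the next one.
- **That AEs are left without a final status.** The physician form has outcome and end-date fields.
- **That the Exit form breaks a promise in section 6.3.** That section says "A record of the reason for withdrawal will be maintained for reporting and publication" without naming the form. Appendix 4 carries a list of reasons with a free-text option, which largely meets it.

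The Appendix 3 wording can also be defended, since it sets a starting point and no end. That is fair; the defect is ambiguity for someone no longer taking the product.

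**Conclusion.** The point holds in a limited form. Section 4.3 is not wrong and nothing contradicts it; the collection plan does not follow through on it. For subjects withdrawn at or soon after stopping ST, no AE contact is defined after exit, and AE incidence after stopping is under-ascertained in them. The size of this group cannot be derived from the protocol, and neither can the number of events missed.

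For subjects who stop and stay, the loss is in recall and dating, together with a home question that does not clearly extend past the last dose. The mean delay of about 25 days rests on uniform stop dates and exact visit times; it ranges from about 15 to 30 days if stops cluster early or late.

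This is a modest, inexpensive improvement to safety ascertainment. It does not affect the primary objective.

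**What to change.** 1. Unless consent is withdrawn, send one automated REDCap Cloud AE form to every subject who stops ST, whether or not they remain enrolled. Send it once the one-to-two-week period in section 4.3 has passed, ask about events since the last ST use, and have the physician verify the answers in the usual way. Add it to Table 1 and to section 6.3.
2. Reword the Appendix 3 AE question so that it expressly includes the time after stopping, for example by asking about events since starting ST whether or not the subject still takes it.

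Automated e-mails to subjects are already part of the system (sections 3.1 and 8.1), so no visit or procedure is added. The cost is the form change, one short extra questionnaire per subject who stops, and its verification. Some dropouts will not answer, so the number of forms sent and returned should be reported beside the results.
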